10.3 DOSE ESCALATIONS

Patients may be escalated to the next higher dose level of ruxolitinib as per dose levels in Table 2a in the event that a patient's platelet count increases, after Cycle 3 of combined therapy or in case of suboptimal response in the opinion if the investigator. Patients with chronic phase MF will escalate the dose of enasidenib from 50mg to 100 mg in cycle 2 and ongoing if platelet count stays above 50,000 at the end of cycle 1 (Table 3a) and no other therapy emergent SAE of grade \geq 2 developed (except grade 2 hyperbilirubinemia that is permitted).

Dose of ruxolitinib and enasidenib cannot be simultaneously increased in the same cycle. Dose escalation is permitted if *ALL* of the following criteria are met:

- 1. No dose reductions due to toxicity were required in the prior cycle
- 2. No dose interruptions due to toxicity were required in the prior cycle
- 3. The prior cycle was not delayed due to toxicity
- 4. The current cycle is not delayed due to toxicity

A Phase II Open-label Study of Combined Ruxolitinib and Enasidenib Sinai in Patients with Accelerated/Blast-phase Myeloproliferative Neoplasm or Chronic-

phase Myelofibrosis with an IDH2 Mutation

(Myeloproliferative Neoplasms Research Consortium [MPN-RC] 119)

5. ANC $\geq 1.0 \times 10^{9}/L$

MPN-RC

- 6. The patient has sub-optimal benefit, defined as a failure to reduce palpable spleen length by at least 50% and/or suboptimal improvement in disease- related symptoms as assessed by the Investigator.
- 7. No development of new on set transfusion dependency judged to be due to therapy

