(Myeloproliferative Neoplasms Research Consortium [MPN-RC] 119)

observed, or at the discretion of the treating physician. Patients will have an end of study visit for a safety follow-up at 30 days after their last dose of therapy.

10.1 DOSE MODIFICATION FOR NON-HEMATOLOGICAL AE'S, CLINICALLY SIGNIFICANT IN THE OPINION OF THE TREATING PHYSICIAN

Based on available pharmacokinetic and drug metabolism data, ruxolitinib is mainly metabolized by CYP3A4 with additional contribution from CYP2C9. Enasidenib inhibits CYP2C9 and induces CYP3A4. Although no adjustment is recommended when ruxolitinib is co-administrated with CYP3A4 inducer, potential drug-drug interactions might occur. This study will be the first time ruxolitinib and enasidenib will be used in combination for this patient population. Therefore, the safety of the combination will be confirmed in the first six patients who accrue. If no more than one patient out of the initial six has a treatment-related Grade 3 or higher adverse event attributable to the study drugs, the combination therapy will be considered safe. If more than one patient out of the initial six has limiting toxicity, the trial will be suspended, and the safety data will be further reviewed.

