 - If Grade 4 (QTcF> 500 msec or > 60 msec change from baseline with torsade de pointes or polymorphic ventricular tachycardia or signs/symptoms of serious arrhythmia), subjects should be admitted to hospital when QTc prolongation is first observed for continuous cardiac monitoring and be discharged only after review by a cardiologist. Dosing with enasidenib should be permanently discontinued.

10.1.2ABNORMAL LEVEL OF LIVER ENZYMES(HYPERBILIRUBINEMIA)

Subjects with elevations in $ALT \ge 3$ -fold ULN, subjects will be monitored using the algorithm:

- Repeat LFT (i.e., ALT, AST, total bilirubin, ALP, GGT) within < 3 days of the initial test. Follow-up 2-3 times weekly, and weekly when stable.
- Perform additional diagnostic follow up:
 - Focused medical history, including review of prior history of liver or biliary disorders, concurrent symptoms, review of all concomitant medications (e.g., acetaminophen-containing medications, over-the-counter or herbal medications, nutritional supplements) including any changes in medications, detailed review of alcohol use.
 - Hepatitis serology (anti-HAV, HBsAg, anti-HBs, anti-HB core, anti-HCV, HCV RNA, EBV and CMV screen), and autoantibodies (e.g., ANA, anti-smooth muscle antibody).
 - Complete physical examination.
 - Liver ultrasound and follow-up imaging as appropriate.
 - Additional evaluation as appropriate (INR, PT).

Hyperbilirubinemia generally decreased in frequency as enasidenib treatment continued. $\$

in Patients with Accelerated/Blast-phase Myeloproliferative Neoplasm or Chronicphase Myelofibrosis with an IDH2 Mutation

(Myeloproliferative Neoplasms Research Consortium [MPN-RC] 119)

 Table 1. Ruxolitinib initial dose for patients' baseline platelet count by cohort*

Cohort	Plt>100 X10 ⁹ /L	Plt 50-100 X10 ⁹ /L	Plt 20-50 X10 ⁹ /L	Plt<20 X10 ⁹ /L
Blast/Accelerated Phase	20 BID	15 BID	10 BID	5 BID
Chronic Phase	15 BID	10 BID**	NA	NA

*Patients already receiving Ruxolitinib will begin trial at the dose they were on prior to combination therapy. **Chronic phase patients with platelet<75 will not be enrolled to the trial.

Table 2a. Ruxolitinib Dose Adjustment for patients with accelerated and blast phase MF for NON-HEMATOLOGICAL AEs*

Dose level	PATIENTS' BASELINE PLATELET COUNTS			
	Plt>100 X10 ⁹ /L	Plt 50-100 X10 ⁹ /L	Plt 20-50 X10 ⁹ /L	Plt<20 X10 ⁹ /L
+1	25 BID	20 BID	NA	NA
0	20 BID	15 BID	10 BID	5 BID
-1	15 BID	10 BID	5 BID	5QD
-2	10 BID	5 BID	5 QD	Stop treatment
-3	5 BID	5 QD	Stop treatment	

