-4	5 QD	Stop treatment		
-5	Stop treatment			

* For patients with accelerated and blast phase MF, treatment will continue at the same dose regardless of platelet count.

Table 2b. Ruxolitinib Dose Adjustment for patients with chronic phase MF for thrombocytopenia or nonhematological AEs

Dos	e level	DOSE ADJUSTMENT FOR THROMBOCYTOPENIA		
		Plt>100 X10 ⁹ /L	Plt 50-100 X10 ⁹ /L	Plt 20-50 X10 ⁹ /L
	+1	20 BID	15 BID	N/A
DOSE ADJUSTMENT FOR NON- HEMATOLOGICAL AES	15 BID	10 BID	5 BID*	
	-1	10 BID	5 BID	5 QD
	-2	5 BID	5 QD	Stop treatment
	-3	5 QD	Stop treatment	
	-4	Stop treatment		

MPN-RC

A Phase II Open-label Study of Combined Ruxolitinib and Enasidenib Sinai in Patients with Accelerated/Blast-phase Myeloproliferative Neoplasm or Chronic-

phase Myelofibrosis with an IDH2 Mutation

(Myeloproliferative Neoplasms Research Consortium [MPN-RC] 119)

 Table 3a. Enasidenib Dose Adjustment for thrombocytopenia

MF chronic phase Cycle 1	MF chronic phase Cycle 2 and above	MF chronic phase Cycle 2 and above	MF chronic phase Cycle 2 and above	MF accelerated phase and blast phase
Platelet >75X10 ⁹ /L	Platelet > 50X10 ⁹ /L	Platelet 35-50X10 ⁹ /L	Platelet<35X10 ⁹ /L	Any platelet count
50mg	100mg	50mg	Hold	100mg

Table 3b. Enasidenib Dose Adjustment for non-hematological AE

Dose Level	Enasidenib
-1	50 mg QD
0	100 mg QD

MPN-RC

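### Section 10.3 ties ruxolitinib escalation to the accelerated/blast-phase Table 2a alone, which leaves chronic-phase patients on the wrong ladder or with no escalation rule

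*Combined protocol and SAP*

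**What the plan says.** Section 10.3 opens with the ruxolitinib rule: "Patients may be escalated to the next higher dose level of ruxolitinib as per dose levels in Table 2a". The triggers are a rise in platelet count, completion of Cycle 3, or a suboptimal response. No cohort is named and no other ruxolitinib table is cited. The next sentence deals with chronic phase: "Patients with chronic phase MF will escalate the dose of enasidenib from 50mg to 100 mg in cycle 2", subject to platelet and toxicity conditions. Two safeguards follow. The first is that "Dose of ruxolitinib and enasidenib cannot be simultaneously increased in the same cycle". The second is a list of seven criteria that must all be met, beginning with "No dose reductions due to toxicity were required in the prior cycle".

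The two dose tables are cohort-specific. Table 2a is headed "Ruxolitinib Dose Adjustment for patients with accelerated and blast phase MF for NON-HEMATOLOGICAL AEs", with columns by baseline platelet count. Table 2b is headed "Ruxolitinib Dose Adjustment for patients with chronic phase MF for thrombocytopenia" or non-hematological AEs, and its columns are labelled as adjustment for thrombocytopenia. The footnote to Table 1 adds that "Patients already receiving Ruxolitinib will begin trial at the dose they were on prior to combination therapy".

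**The concern.** The escalation rule and the table structure do not fit together. The protocol sets two ruxolitinib ladders, and the chronic-phase one stops lower. The only sentence that authorises going up a ladder names the accelerated/blast-phase table and applies it to patients in general. The section is plainly not confined to accelerated/blast phase, because its next sentence sets the chronic-phase enasidenib step and its benefit criterion (spleen length and symptoms) carries no cohort limit. By contrast, the toxicity rules in Sections 10.1 and 10.2 cite both tables.

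What is at stake is dosing in the chronic-phase cohort. Ruxolitinib in that cohort is limited by platelet count: Table 2b adjusts for thrombocytopenia, and Section 10.2 stops the drug below 20 × 10⁹/L. In accelerated/blast phase, treatment continues whatever the count. Section 18.3 lists ruxolitinib thrombocytopenia as dose-related, and Section 10.1 says of the combination: "This study will be the first time ruxolitinib and enasidenib will be used in combination for this patient population". There is also a reporting consequence. Section 16.7 treats anything above the assigned dose as an overdose, so whether 25 mg BID in a chronic-phase patient counts as one depends on which table governs.

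**Working it through.** The plan gives no figure of its own to reproduce; the check is a comparison of the tables.

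**Inputs (ruxolitinib, mg BID; platelets × 10⁹/L)**

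| Source | >100 column | 50–100 column |
|---|---|---|
| Table 1, chronic-phase start | 15 | 10 |
| Table 2a, level −1 | 15 | 10 |
| Table 2a, level 0 | 20 | 15 |
| Table 2a, level +1 | 25 | 20 |
| Table 2b, row below +1 | 15 | 10 |
| Table 2b, level +1 | 20 | 15 |

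**The columns do not mean the same thing.** Table 2a is indexed by baseline count. Table 2b has a 20–50 column, yet chronic-phase patients need at least 75 at entry (Section 8.1, item 5; Table 1 footnote). That column cannot be a baseline count, so Table 2b must be read by the count on treatment. Subtracting same-named columns is valid only when baseline and current counts fall in the same band.

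**Literal reading: chronic phase follows Table 2a.** Excess = top dose on Table 2a (baseline column) minus top dose on Table 2b (current column).

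1. *Baseline and current platelets >100, Table 1 start.* Table 2a path: 15 → 20 → 25. Table 2b path: 15 → 20.
   - After step 1: 20 − 20 = 0.
   - After step 2: 25 − 20 = 5 mg BID, that is 50 against 40 mg/day; 50/40 = 1.25.
2. *Baseline and current platelets >100, entry on an existing 20 mg BID.* One Table 2a step gives 25. Table 2b has no row above 20. Excess: 25 − 20 = 5 mg BID after one step. Entry doses are not given in the documents, so this case is an illustration.
3. *Baseline 75–100, platelets remain at 50–100, Table 1 start.* Table 2a path: 10 → 15 → 20. Table 2b path: 10 → 15.
   - After step 1: 15 − 15 = 0.
   - After step 2: 20 − 15 = 5 mg BID, that is 40 against 30 mg/day; 40/30 = 1.33.
4. *Baseline 75–100, platelets rise above 100.* Table 2a stays in its 50–100 column and tops out at 20. Table 2b moves to its >100 column and also tops out at 20. Excess: 20 − 20 = 0. A rising platelet count is one of the triggers in Section 10.3, so this case is a realistic one.

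**Title-limited reading: Table 2a's heading confines the sentence to accelerated/blast phase.** The question is then whether any other text sends chronic-phase escalation to Table 2b. Section 10.1 cites both tables for non-hematologic toxicity, and Section 10.2 cites both for hematological adverse events. Neither is an escalation rule. The +1 row of Table 2b is then never invoked, and chronic-phase ruxolitinib escalation has no rule.

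**Exposure.** Section 11.4 caps the chronic-phase cohort at 10 enrolled patients. The number who would meet all seven criteria, once or twice, cannot be derived from the documents.

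**The case against.** The best reply is that the text can be read consistently. Table 2a's own title restricts it, so the first sentence of Section 10.3 would cover ruxolitinib in accelerated/blast phase and the second would cover enasidenib in chronic phase. On that view the defect is an omission, not permission to overdose. This is a fair reading and it stands as an alternative. It does not rescue the section, because it leaves Table 2b with an escalation row that nothing calls on. Either reading needs the same correction.

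Three further points stand and limit the size of the concern.

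- From the Table 1 start the excess needs two steps. Section 10.3 refers to the next level in the singular and is silent on repeat steps. It sets no cap, but all seven criteria would have to be met again.
- The +1 row of Table 2b is not a firm ceiling. Patients already on ruxolitinib keep their dose and no upper limit on that dose is stated, so a dose above the row is not in itself a breach of a stated maximum.
- Protection remains in place: only one drug may be raised in a cycle, and Table 2b reductions for thrombocytopenia still apply.

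A reader might infer that chronic-phase patients go 5 mg BID too high at the first escalation. That would require reading the next level by label, from the chronic-phase starting row straight to Table 2a's +1. On Table 2a's own ladder the step above 15 is 20 and the step above 10 is 15, the same doses as Table 2b's +1 row. A reader might also take the 33% excess as general for patients with platelets of 50–100. It holds only if the count stays in that band, as case 4 of the working shows.

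**Conclusion.** The concern holds as a wrong or incomplete table reference in Section 10.3. As written, chronic-phase patients are either sent to the accelerated/blast-phase ladder or left without a ruxolitinib escalation rule.

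On the literal reading the possible excess over Table 2b is 5 mg BID (10 mg/day). It is 25% where baseline and current platelets exceed 100, and 33% where baseline is 75–100 and the count stays at 50–100. It is nil after the first step from the Table 1 start, and nil where a baseline of 75–100 rises above 100. These figures assume that Table 2b is read by on-treatment count and that Section 10.3 allows more than one step; the one-step route assumes an entry dose of 20 mg BID with platelets above 100.

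The documents do not show that any patient will receive the higher dose, or that a defined maximum would be broken. The matter concerns dosing safety and clarity in a descriptive cohort of at most 10 patients. The Simon design for accelerated/blast phase and the Gehan rule for chronic phase are unaffected.

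**What to change.** In the first sentence of Section 10.3, replace the reference to Table 2a with: Table 2a (accelerated/blast phase) or Table 2b, by current platelet count (chronic phase). The chronic-phase top level is then 20 mg BID above 100 × 10⁹/L and 15 mg BID at 50–100. A patient whose retained entry dose already equals or exceeds the applicable +1 dose has no higher row and would not be escalated.

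The cost is one line in an amendment. Design, sample size and analysis stay as they are.

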10.4 CONCOMITANT MEDICATIONS/TREATMENTS

All supportive measures consistent with optimal subject care will be given throughout the study. Concomitant medications will be captured in the Case Report Form (CRF) beginning at Screening. Packed red blood cell or platelet transfusions are allowed when necessary. Growth factor use (including erythropoietin) is not allowed with the exception of the use of filgrastim (G-CSF) or pegfilgrastim, which is permitted ONLY when used to treat febrile neutropenia or in patients who have prolonged (one week or more) Grade 3-4 neutropenia, after approval from the Study Chair.

Concurrent use of strong inducers of CYP3A4 (Rifampin, St. John's Wort, carbamazepine, phenytoin) and/or the following strong inhibitors of CYP3A4 (protease inhibitor containing HIV antiretrovirals, cobicistat, clarithromycin, itraconazole, ketoconazole, nefadozone, and telithromycin) are prohibited. Also prohibited are CYP2C9 substrate medications that have a narrow therapeutic range: phenytoin and warfarin.

The following medications that are known to prolong QT interval are prohibited: amiodarone, arsenic trioxide, astemizole, azithromycin, bepridil, chloroquine, chlorpromazine, cisapride, citalopram, clarithromycin, disopyramide, dofetilide, domperidone, droperidol, erythromycin, escitalopram, flecainide, halofantrine, haloperidol, ibutilide, levomethadyl, mesoridazine, methadone, moxifloxacin, pentamidine, pimozide, probucol, procainamide, quinidine, sevoflurane, sotalol, sparfloxacin, terfenadine, thioridazine, or vandetanib.

Concomitant use of other cytotoxic chemotherapeutic agents (e.g. anagrelide) or other experimental drug or therapy while the subject is on study is prohibited, except for hydroxyurea.

Patients will be permitted to receive hydroxyurea while on study for a total of 3 cycles of combined therapy to control leukocytosis and thrombocytosis at the discretion of the treating physician. Patients who enter study on hydroxyurea will be permitted to remain on hydroxyurea for a total of 3 cycles of combined therapy. Patients who continue to require hydroxyurea after 3 cycles will be removed from study.

Steroids are allowed for the treatment of IDH-Inhibitor Differentiation Syndrome (IDH-DS), if warranted, as standard of care. The use of chronic low-dose steroids to treat an underlying medical condition that is not a malignancy is permitted during the course of study treatment

For patient's requiring ant-fungal prophylaxis, intravenous micafungin is the preferred agent. If micafungin is not feasible, the oral antifungal of choice would be posaconazole barring other patient specific factors that would preclude use of posaconazole.

Given the solubility profile of enasidenib, the exposure can be much lower for subjects with elevated gastric pH. Thus antacids, H2 blockers, or proton pump inhibitors should be used only if medically necessary and with at least 4 hours of elapsed time after enasidenib administration.

As enasidenib is an inhibitor of UGT1A1, the metabolism of drugs that are substrates for UGT1A1, including ezetimibe, raloxifene and raltegravir, may be slowed, leading to increased exposure to these compounds. Therefore, subjects on these drugs should be switched to lower doses or alternate therapies, if possible, or otherwise monitored for AEs associated with the respective products and elevations in bilirubin levels.

10.5 IDH-INHIBITOR DIFFERENTIATION SYNDROME (IDH-DS)

in Patients with Accelerated/Blast-phase Myeloproliferative Neoplasm or Chronicphase Myelofibrosis with an IDH2 Mutation

(Myeloproliferative Neoplasms Research Consortium [MPN-RC] 119)

Subjects treated with enasidenib may develop signs and symptoms of a IDH-Inhibitor Differentiation Syndrome (IDH-DS). This may include any of the following: unexplained fever, skin rash, leukocytosis, thrombocytosis, hypoxia, respiratory distress, interstitial pulmonary infiltrates, pleural and/or pericardial effusion, peripheral edema, weight gain, or clinical deterioration. No single sign or symptom may be considered per se as diagnostic of the syndrome. It is recommended that the prophylactic and therapeutic measures indicated below be undertaken at the earliest manifestations of suspected IDH-Inhibitor Differentiation Syndrome (IDH-DS):

- Enasidenib may be held at the Investigator's discretion, and must be held if severe symptoms persist after 48 hours of systemic steroid administration.
- Prompt initiation of hydroxyurea at a suggested dose of 2 to 3 g PO two or three times daily.
- Prompt administration of corticosteroids at a suggested dose of 10 mg of dexamethasone intravenously (IV) every 12 hours until the disappearance of symptoms and signs, and for a minimum of 3 days.
- Initiation of furosemide per local standard practice, if clinically required.
- Prompt initiation of leukapheresis, if clinically required.

Once the signs and symptoms resolve and the subject's clinical condition improves, enasidenib may be reinitiated. The dose of enasidenib at re-initiation is to be discussed with the Study Chair.

For more information See Appendix D.

MPN-RC

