Signs and symptoms could include fever, dyspnea, edema/ weight gain, increased serum creatinine and, in some cases, clinical features consistent with the acute respiratory distress syndrome with associated bilateral pulmonary infiltrates, and pulmonary or pericardial effusions. Increases in white blood cell (WBC) count concurrent to DS has been observed, but by itself do not substantiate the syndrome.

There is no pathognomonic clinical sign or laboratory test to diagnose DS. In some instances, clinical presentation of DScan be confounded by other medical condition(s), such as concurrent infections or heart failure. Consequently, diagnosis of DS is made by excluding other potential causes, rather than based on a specific set of signs and symptoms.

To improve diagnostic and treatment practices for management of DS associated with treatment with IDH-inhibitors (IDH DS), data for adverse events meeting diagnostic criteria for DS will be reviewed and assessed by a Differentiation Syndrome Review Committee.

Clinical Assessment of Subjects for signs and symptoms of IDH-inhibitors differentiation syndrome

Due to the heterogeneity of clinical symptoms and differences in adverse events reporting practices (e.g., symptoms of suspected IDH DS reported in place of DS diagnosis), exact incidence of Differentiation Syndrome in subjects treated with IDH-inhibitors has not been determined. In the clinical trial conducted for Idhifa's approval, at least 14 percent of patients experienced differentiation syndrome

As it has been reported by the Study Investigators, IDH DS is more likely to manifest within 10 days to 5 months after the start of treatment, or after re-initiation of the study drug following prolonged treatment interruption (e.g., >3 weeks) in subjects who are not in complete remission. In some cases, symptoms re-appeared after cessation of treatment for the initial manifestation of IDH DS.

Signs and Symptoms

In clinical trials with IDH inhibitors, DS has been described in two categories of severity:

MPN-RC A Phase II Open-label Study of Combined Ruxolitinib and Enasidenib Sinai in Patients with Accelerated/Blast-phase Myeloproliferative Neoplasm or Chronic-

phase Myelofibrosis with an IDH2 Mutation

(Myeloproliferative Neoplasms Research Consortium [MPN-RC] 119) Severe IDH-Differentiation Syndrome

Based on presence of any of the below listed factors, with, or without symptoms of moderate severity IDH DS

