- The study drug may be withheld at the investigator's discretion. Due to long half-life of the IDH-inhibitors, treatment interruption may not immediately reverse symptoms of IDH DS. Potential for drug-drug interaction between IDH inhibitor and treatments initiated for management of IDH DS should be considered, when making decisions about study drug treatment interruption. If interrupted, study drug treatment may be reinitiated at the original or reduced dose once the signs and symptoms resolve and the subject's clinical condition improves.

A Phase II Open-label Study of Combined Ruxolitinib and Enasidenib Sinai

in Patients with Accelerated/Blast-phase Myeloproliferative Neoplasm or Chronicphase Myelofibrosis with an IDH2 Mutation

(Myeloproliferative Neoplasms Research Consortium [MPN-RC] 119)

- If renal dysfunction or severe pulmonary symptoms requiring intubation or ventilator support persist for more than 48 hours after initiation of systemic corticosteroids, interrupt enasidenib treatment until signs and symptoms are no longer severe
- In subjects with elevated WBC, prompt initiation of hydroxyurea is suggested, as per standard local practices (e.g., dose of 2 to 3g PO twice or three times daily for WBC >30x10⁹/L)
- In cases of severe leukocytosis, use of leukapheresis may be appropriate
- For substantial fluid accumulation, initiation of furosemide may be appropriate, as per local standard practice
- Pericardial effusion a less common symptom of IDH DS can be life threatening condition requiring urgent intervention
- Subjects with increasing serum creatinine levels should be evaluated for TLS
- Subjects experiencing rapid increase in peripheral blood cells should be monitored for disseminated intravascular coagulopathy and hemorrhages
- Imaging techniques such as standard or high-resolution CT or chest X-ray are useful in establishing a diagnosis of IDH DS. However, chest X-ray is less sensitive in detecting early radiological signs of IDH DS associated changes.

Immediate communication with the Study Co-Chairs is encouraged for guidance regarding treatment.

MPN

Mount The Ti A Phase II Open-label Study of Combined Ruxolitinib and Enasidenib Sinai in Patients with Accelerated/Blast-phase Myeloproliferative Neoplasm or Chronicphase Myelofibrosis with an IDH2 Mutation

(Myeloproliferative Neoplasms Research Consortium [MPN-RC] 119)

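### Section 10.5 recommends hydroxyurea for suspected differentiation syndrome with no white-cell condition, while Appendix D conditions it on a raised white cell count

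*Combined protocol and SAP*

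**What the plan says.** Four places in the combined protocol and SAP deal with hydroxyurea on study.

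- **Section 10.5 (IDH-DS).** A list of measures is recommended as soon as the syndrome is first suspected. One item is "Prompt initiation of hydroxyurea at a suggested dose of 2 to 3 g PO two or three times daily". It carries no WBC condition. Other items in the same list do carry a condition, for example "Prompt initiation of leukapheresis, if clinically required", and the furosemide item is qualified in the same way. The section ends by referring to Appendix D.
- **Appendix D (34.4, IDH-DS guidance).** The trigger is the same, but the text reads "In subjects with elevated WBC, prompt initiation of hydroxyurea is suggested, as per standard local practices". The same dose is given as an example for WBC above 30 × 10⁹/L.
- **Section 10.6 (leukocytosis without IDH-DS).** The WBC condition and example dose are the same as in Appendix D.
- **Section 10.4 (concomitant treatment).** Hydroxyurea is permitted for a total of three cycles "to control leukocytosis and thrombocytosis at the discretion of the treating physician". For the syndrome itself, 10.4 names a different drug class: "Steroids are allowed for the treatment of IDH-Inhibitor Differentiation Syndrome (IDH-DS), if warranted, as standard of care".

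**The concern.** Three of the four places tie hydroxyurea to blood counts, and Section 10.5 does not. For a patient with suspected IDH-DS and a high WBC, all four agree in practice. For a patient with suspected IDH-DS and no raised WBC, 10.5 recommends starting 4 to 9 g/day, while Appendix D gives no recommendation to start it.

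Hydroxyurea is given here to bring counts down. In a patient whose counts are not raised, it adds myelosuppression. The AP/BP cohort is the most exposed. The platelet minimum in Section 8.1 applies to chronic-phase patients only, and no neutrophil minimum is listed. Table 1 gives a ruxolitinib starting dose for AP/BP patients with platelets below 20 × 10⁹/L, and Section 10.2 keeps study drug at the same dose in these patients whatever the platelet or neutrophil count. A site following 10.5 as written could add a cytoreductive drug where a site following Appendix D would give corticosteroids and watch the WBC.

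**Working it through.** **1. Daily dose implied by Section 10.5.** The section states a dose and a frequency but no daily total.

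| Dose | Twice daily | Three times daily |
|---|---|---|
| 2 g | 4 g | 6 g |
| 3 g | 6 g | 9 g |

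The range is 4 to 9 g/day. Section 10.5 gives no duration for hydroxyurea, so no total course dose can be derived. The three-day minimum in that list belongs to dexamethasone.

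**2. Do the two IDH-DS texts cover the same situation?**

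| | Section 10.5 | Appendix D |
|---|---|---|
| Syndrome | IDH-DS | IDH-DS |
| Trigger | first signs, suspected | first signs, suspected |
| Dexamethasone | 10 mg IV every 12 h | 10 mg IV every 12 h |
| Hydroxyurea dose | 2–3 g, two or three times daily | 2–3 g, two or three times daily, as an example |
| Condition on hydroxyurea | none | elevated WBC (example: > 30 × 10⁹/L) |

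The condition on hydroxyurea is the relevant difference.

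**3. Can the patient in question occur under the protocol's own definitions?** Appendix D lists three severe factors, any one of which suffices, and six moderate factors, of which at least two are needed. WBC is in none of the three and none of the six. Leukocytosis appears separately, as something that commonly accompanies the syndrome. Appendix D adds: "Increases in white blood cell (WBC) count concurrent to DS has been observed, but by itself do not substantiate the syndrome". In Section 10.5 leukocytosis is one of several possible signs and is not required. IDH-DS without a raised WBC is therefore allowed for, although the word commonly suggests it is not the usual picture.

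**4. How many patients?** Inputs:

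- 24 of 330 subjects with IDH-DS reported as a serious event in the enasidenib study described in Section 6.3: 24/330 = 7.3%.
- At least 14% with differentiation syndrome in the approval trial (Appendix D).
- 20 evaluable AP/BP patients (Section 21).

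Expected IDH-DS cases: 0.073 × 20 = 1.46 and 0.14 × 20 = 2.8, or about 1.5 to 2.8 patients.

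The lower rate counts serious events only, and the higher is stated as a minimum. The Section 6.3 study enrolled AML and MDS patients, and the approval was for relapsed or refractory AML. Applying either rate to MPN patients who also take ruxolitinib is an assumption. The number with the syndrome but no leukocytosis is some part of 1.5 to 2.8, and the documents do not give the fraction.

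**The case against.** The strongest reply is that this is one missing phrase between two sets of advice. The measures in 10.5 are recommended and the dose is suggested. Appendix D says each case should be managed individually. An investigator is free to withhold hydroxyurea when the WBC is normal, and most might. This stands, and it limits the harm. It does not tell a site which text to follow.

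A second reply is that 10.5 describes its measures as prophylactic as well as therapeutic, and 10.6 warns of rapid WBC expansion, so early hydroxyurea before the count rises may be intended. That is possible. But 10.5 does not say so, and Appendix D, with the same trigger, does not recommend it. The two texts would still need reconciling.

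Several stronger readings are tempting, and the documents do not support them.

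- **That 10.4 forbids hydroxyurea for IDH-DS without raised counts.** It states a purpose but does not say that other uses are barred. Exclusion criterion 1a allows up to three cycles without naming an indication, and 10.4 opens by allowing supportive measures generally. Appendix D likewise conditions its suggestion without prohibiting other use.
- **That hydroxyurea under 10.5 is open-ended.** 10.5 gives no stopping point, but 10.4 limits the total: "Patients who continue to require hydroxyurea after 3 cycles will be removed from study".
- **That the 23.9% rate of serious febrile neutropenia in Section 6.3 measures exposure, because fever is a listed sign.** Section 10.5 says no single sign is diagnostic. Appendix D makes IDH-DS a diagnosis of exclusion, asks for two factors for moderate disease, and directs that conditions refractory to initial treatment, or worsening within 48 hours, be managed as potential IDH-DS. A neutropenic patient with new fever would first be suspected of infection.
- **That hydroxyurea cytopenias would distort the six-patient safety check.** Section 10.1 says cytopenias in themselves are not adverse events, apart from grade 4 neutropenia with fever unresolved within 14 days and grade 4 thrombocytopenia with significant bleeding. Any effect is confined to those two exceptions and cannot be sized from the documents.

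**Conclusion.** The inconsistency is real and is in the current text. For suspected IDH-DS without a raised WBC, Section 10.5 recommends hydroxyurea at 4 to 9 g/day and Appendix D does not. The dose arithmetic is exact, and the conflict follows from reading the two sections together.

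The size is small: a fraction of roughly 1.5 to 2.8 IDH-DS cases among 20 AP/BP patients, resting on AML/MDS rates carried over by assumption and on an unstated share without leukocytosis. Investigator discretion reduces it further. This is a patient-safety clarification. The response endpoint, the two-stage decision rule and the planned analyses are not shown to be affected. It is worth correcting because the patient is foreseeable under the protocol's own definitions, may already be cytopenic, and one added condition resolves the conflict.

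**What to change.** In Section 10.5, put Appendix D's condition in front of the existing bullet: *In subjects with elevated WBC (e.g., > 30 × 10⁹/L)*, followed by the current words "Prompt initiation of hydroxyurea at a suggested dose of 2 to 3 g PO two or three times daily". Leave the corticosteroid bullet as it is, unconditional, so that steroids are not delayed. If pre-emptive hydroxyurea is in fact intended, the alternative is to say so in 10.5 with the reason and to change Appendix D and 10.4 to match.

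No further change is needed for this point. A flat prohibition without leukocytosis, or new counting rules in 10.4, would go beyond the inconsistency.

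Cost: one added phrase. The drawback is that hydroxyurea waits for a WBC result. Table 4 already schedules a CBC with differential weekly in cycles 1 and 2 and on day 1 of each later cycle. An event between visits from cycle 3 onward may need an unscheduled CBC. No added patients or scheduled visits are required.
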